#### **8.3.3. Electrocardiograms**

- A single 12-lead ECG will be obtained as indicated in the SoA (Section 1.3).
- Measurements to be collected will include the following: HR and PR, QRS, and QT intervals.
- The investigator must review the ECG recordings and document this review. All ECG reports must be filed with the source documents.

#### **8.3.4. Clinical Laboratory Assessments**

- [Appendix 2](#) provides the list of clinical laboratory tests to be performed, and the SoA (Section 1.3) details the timing and frequency.
- The investigator must review the laboratory report and document this review. Laboratory reports must be filed with the source documents.
- All protocol-required laboratory tests, as defined in [Appendix 2](#), must be conducted in accordance with the laboratory manual and the SoA (Section 1.3).
- If laboratory values from non-protocol-specified laboratory tests performed at the institution's local laboratory require a change in participant management or are considered clinically significant by the investigator (eg, SAE, AE, or dose modification), then the results must be recorded.

#### **8.3.5. Pregnancy Testing**

- Section 5.1 Inclusion Criteria details the pregnancy testing entry criteria.
- Pregnancy testing (urine or serum as required by local regulations) should be conducted at certain visits during intervention, as specified in the SoA (Section 1.3).

- Pregnancy testing (urine or serum as required by local regulations) should be conducted at the end of relevant systemic exposure (ie, at the EOT or E/D visit, as specified in the SoA [Section 1.3]).
- Additional serum or urine pregnancy tests may be performed, as determined necessary by the investigator or required by local regulation, to establish the absence of pregnancy at any time during the participation in the study.

#### **8.3.6. Suicidal Ideation and Behavior Risk Monitoring**

XYWAV and twice-nightly high-sodium oxybate treatments (eg, XYREM) are considered central nervous system depressants.

When informed consent or assent has been given, families and caregivers of participants being treated with XYWAV should be alerted regarding the need to monitor participants for the emergence of unusual changes in behavior, as well as the emergence of suicidal ideation and behavior and to report such symptoms immediately to the study investigator.

At screening, the Baseline-Screening version of the C-SSRS will be administered to participants to exclude any individuals with active suicidal ideation and/or behavior. The C-SSRS must be administered by a qualified site rater who has received training in its administration. If active suicidal ideation (eg, a positive response to Question 4 or 5 on the C-SSRS) or behavior (eg, a positive response to any suicidal behavior question on the C-SSRS) is noted, a same-day evaluation should be conducted by a trained mental health practitioner, and the sponsor or designee should be contacted to discuss the participant's continuation in the study.

Active suicidal ideation or behavior occurring after the participant has initiated study intervention must be recorded as an SAE and reported to the sponsor or designee within 24 hours of first knowledge of the event by study personnel. These participants should also undergo a risk assessment by a trained mental health practitioner.

All factors contributing to suicidal ideation and/or behavior should be evaluated and consideration should be given to discontinuation of study intervention.

#### **8.4. Adverse Events, Serious Adverse Events, and Other Safety Reporting**

The definitions of AEs and SAEs are provided in [Appendix 3](#).

The definitions of unsolicited and solicited AEs are provided in [Appendix 3](#).

The investigator and any qualified designees are responsible for detecting, documenting, and recording events that meet the definition of an AE or SAE and remain responsible for following up all AEs. This includes events reported by the participant (or, when appropriate, by a caregiver, surrogate, or the participant's legally authorized representative).

The method of recording, evaluating, and assessing causality of AEs and SAEs and the procedures for completing and transmitting SAE reports are provided in [Appendix 3](#).

#### **8.4.1. Time Period and Frequency for Collecting AE and SAE Information**

All AEs and SAEs will be collected from the start of intervention until the follow-up visit at the time points specified in the SoA (Section 1.3).

Note: All SAEs that occur after the consent form is signed but before study intervention/treatment must be reported by the investigator if they cause the participant to be excluded from the study or are the result of a protocol-specified intervention, including but not limited to washout or discontinuation of usual therapy, diet, placebo treatment, or a procedure.

Medical occurrences that begin before the start of study intervention but after obtaining informed consent will be recorded as medical history/current medical conditions, not as AEs.

All SAEs will be recorded and reported to the sponsor or designee within 24 hours of first knowledge of the event by study personnel, as indicated in [Appendix 3](#). The investigator will submit any updated SAE data to the sponsor within 24 hours of it being available.

Investigators are not obligated to actively seek information on AEs or SAEs after conclusion of study participation. However, if the investigator learns of any SAE, including a death, at any time after a participant has been discharged from the study and they consider the event to be reasonably related to the study intervention or study participation, the investigator should promptly notify the sponsor.

#### **8.4.2. Method of Detecting AEs and SAEs**

Care will be taken not to introduce bias when detecting AEs and/or SAEs. Open-ended and nonleading verbal questioning of the participant is the preferred method to inquire about AE occurrences.

#### **8.4.3. Follow-up of AEs and SAEs**

After the initial AE/SAE report, the investigator is required to proactively follow up with each participant at subsequent visits/contacts. All SAEs will be followed up until resolution or stabilization, the event is otherwise explained, or the participant is lost to follow-up (as defined in Section 7.3). Further information on follow-up procedures is provided in [Appendix 3](#).

#### **8.4.4. Regulatory Reporting Requirements for SAEs**

- Prompt notification from the investigator to the sponsor of an SAE is essential so that legal obligations and ethical responsibilities regarding the safety of participants and the safety of a study intervention under clinical investigation are met.
- The sponsor has a legal responsibility to notify both the local regulatory authority and other regulatory agencies about the safety of a study intervention under clinical investigation. The sponsor will comply with country-specific regulatory requirements related to safety reporting to the regulatory authority, IRB/IEC, and investigators.
- An investigator who receives an investigator safety report describing an SAE or other specific safety information (eg, summary or listing of SAEs) from the sponsor will review, file it along with the IB, and notify the IRB/IEC, if appropriate according to local requirements.

- Investigator safety reports will be prepared for suspected unexpected serious adverse reactions according to local regulatory requirements and sponsor policy and forwarded to investigators as necessary. The Reference Safety Information for the determination of expectedness of XYWAV can be found in the IB.

#### **8.4.5. Pregnancy**

- Details of all pregnancies in female participants and female partners of male participants will be collected after the start of study intervention until 7 days after the last dose of study intervention.
- If a pregnancy is reported, the investigator will record pregnancy information on the appropriate form and submit it to the sponsor within 24 hours of learning of the pregnancy of female participant or female partner of male participant (after obtaining the necessary signed informed consent from the female partner).
- Although pregnancy itself is not considered to be an AE or SAE, any pregnancy complication or elective termination of a pregnancy for medical reasons will be reported as an AE or SAE.
- Abnormal pregnancy outcomes (eg, spontaneous abortion, fetal death, stillbirth, congenital anomalies, ectopic pregnancy) are considered SAEs and will be reported as such.
- The participant/pregnant female partner will be followed to determine the outcome of the pregnancy. The investigator will collect follow-up information on the participant/pregnant female partner and the neonate, and the information will be forwarded to the sponsor. Neonates will be followed until 6 months after birth.
- Any poststudy pregnancy-related SAE considered reasonably related to the study intervention by the investigator will be reported to the sponsor as described in Section 8.4.4. Although the investigator is not obligated to actively seek this information in former study participants/pregnant female partners, he or she may learn of an SAE through spontaneous reporting.
- Any female participant who becomes pregnant while participating in the study will discontinue study intervention or be withdrawn from the study.

#### **8.5. Pharmacokinetics**

Pharmacokinetic parameters will not be evaluated in this study.

#### **8.6. Pharmacodynamics**

Pharmacodynamic parameters will not be evaluated in this study.

#### **8.7. Genetics**

Genetics will not be evaluated in this study.

### **8.8. Biomarkers**

Biomarkers will not be evaluated in this study.

### **8.9. Immunogenicity Assessments**

Immunogenicity will not be evaluated in this study.

### **8.10. Medical Resource Utilization and Health Economics**

Medical resource utilization and health economics parameters will not be evaluated in this study.

## 9. STATISTICAL CONSIDERATIONS

The SAP will be finalized before the study start date, and it will include a more technical and detailed description of the statistical analyses described in this section. This section is a summary of the planned statistical analyses of study endpoints.

### 9.1. Statistical Hypotheses

The primary statistical hypothesis for this study is that after switching from twice-nightly high-sodium oxybate to XYWAV, there will be a statistically significant decrease compared to baseline in 24-hour average SBP after 6 weeks ( $H_1: \Delta_{SBP} < 0$ ).

Similarly defined hypotheses will be tested for the secondary endpoints of change in daytime and nighttime average SBP (both assessed using 24-hour ambulatory BP monitors) and change in seated resting SBP (assessed using the measurements performed by the site personnel).

#### 9.1.1. Multiplicity Adjustment

To address the multiplicity issue due to multiple endpoints, a fixed hierarchical testing sequence will be employed. The formal testing procedure will stop when a  $P$  value exceeds the prespecified significance level. Statistical significance for the primary endpoint will be assessed using O'Brien-Fleming alpha levels of 0.00998 at the interim analysis. If the primary endpoint is met at the interim analysis, study enrollment will end and the primary endpoint will not be tested again (see Section 9.4). If the primary endpoint is not met at the interim analysis, study enrollment will continue and the O'Brien-Fleming alpha level of 0.02194 will be used for the final analysis.

The secondary endpoints will be tested only once – at the interim analysis if the primary endpoint is met at the interim analysis, or at the final analysis if the primary endpoint is not met at the interim analysis but is met at the final analysis. In group sequential designs with hierarchical endpoints, typical alpha recycling methods do not conserve the family-wise error rate, and separate error spending functions for primary and secondary endpoints are suggested (Glimm, 2010). For studies in which O'Brien-Fleming alpha levels are used for testing the primary endpoint, the use of Pocock alpha levels for testing secondary endpoints is recommended (Glimm, 2010). Therefore, statistical significance for each of the secondary endpoints will be assessed using the Pocock alpha level of 0.0168 when assessed at either the interim or final analysis.

Statistical hypotheses to be tested (in sequential order):

1. Change in the 24-hour average SBP (mm Hg) following 6 weeks of XYWAV treatment after switching from twice-nightly high-sodium oxybate in participants with narcolepsy
2. Change in the daytime average SBP (mm Hg) following 6 weeks of XYWAV treatment after switching from twice-nightly high-sodium oxybate in participants with narcolepsy
3. Change in the seated resting average SBP (mm Hg) following 6 weeks of XYWAV treatment after switching from twice-nightly high-sodium oxybate in participants with narcolepsy

4. Change in the nighttime average SBP (mm Hg) following 6 weeks of XYWAV treatment after switching from twice-nightly high-sodium oxybate in participants with narcolepsy

Other endpoints will be handled in an exploratory manner and will not be involved in multiplicity adjustment.

## 9.2. Analysis Sets

For the purposes of analysis, the following analysis sets are defined:

Participant Analysis Set	Description
Enrolled Set	The Enrolled Analysis Set will include all participants who provide informed consent for this study.  This analysis set will be used to summarize participant disposition, major protocol deviations (as classified in Clinical Trial Management Software), and inclusion/exclusion from the Safety Set, including reasons for exclusion from it.
Safety Set	All participants who take/receive at least 1 dose of study intervention (XYWAV).  This analysis set will be used for reporting analyses of safety endpoints and sensitivity analyses of efficacy endpoints.
Completer Set	All participants who complete the EOT Visit after 6 weeks of study intervention with a 24-hour BP recording at this visit that meets the minimal data standards.  This analysis set will be used for primary analyses of effectiveness variables.
Effectiveness Set	All participants who complete at least 1 post-baseline study effectiveness assessment (including early discontinuation).  This analysis set will be used for reporting sensitivity analyses of effectiveness endpoints.

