### 3. OBJECTIVES, ENDPOINTS, AND ESTIMANDS

Objectives	Endpoints
Primary Efficacy	
To evaluate the impact of switching from twice-nightly high-sodium oxybate to XYWAV on 24-hour ambulatory SBP for participants with narcolepsy	
The estimand is defined as follows:
 
Treatments: XYWAV
 
Population: Participants with Type 1 or Type 2 narcolepsy, treated with 6 to 9 g (inclusive) of twice-nightly high-sodium oxybate per evening, [REDACTED]
 
Endpoint: Change from baseline to EOT Visit on the 24-hour average SBP (mm Hg)
 
Intercurrent events: Alternative/additional or changes in therapy related to BP as well as discontinuation of treatment due to lack of efficacy, an AE, or any other reason. Definitions for all intercurrent events will be provided. Participants who experience any intercurrent event will be included in the analysis.
 
Summary: Change from baseline to EOT Visit on the 24-hour average SBP (mm Hg)

Secondary Efficacy	
To evaluate the impact of switching from twice-nightly high-sodium oxybate to XYWAV on daytime ambulatory SBP for participants with narcolepsy	
The estimand is defined as follows:
 
Treatments: XYWAV
 
Population: Participants with Type 1 or Type 2 narcolepsy, treated with 6 to 9 g (inclusive) of twice-nightly high-sodium oxybate per evening, [REDACTED]
 
Endpoint: Change from baseline to EOT Visit on the daytime average SBP (mm Hg)
 
Intercurrent events: Alternative/additional or changes in therapy related to BP as well as discontinuation of treatment due to lack of efficacy, an AE, or any other reason. Definitions for all intercurrent events will be provided. Participants who experience any intercurrent event will be included in the analysis.
 
Summary: Change from baseline to EOT Visit on the daytime average SBP (mm Hg)

To evaluate the impact of switching from twice-nightly high-sodium oxybate to XYWAV on seated resting SBP for participants with narcolepsy	
The estimand is defined as follows:
 
Treatments: XYWAV
 
Population: Participants with Type 1 or Type 2 narcolepsy, treated with 6 to 9 g (inclusive) of twice-nightly high-sodium oxybate per evening, [REDACTED]

Objectives	Endpoints

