### **9.3.1.2. Intercurrent Event Strategies**

The following intercurrent events may occur during the study:

- Study intervention discontinuation due to AEs, lack of efficacy, or use of other (prohibited) concomitant medications, etc.
- Withdrawal from the study
- Lost to follow-up
- Change in antihypertensive drug use during the Intervention Period

A Treatment Policy strategy will be used for each specified analysis (ie, the data will be collected and analyzed regardless of whether an intercurrent event has occurred). Participants who do not experience certain intercurrent events while on study (eg, change in antihypertensive drug use) will be included in a sensitivity analysis.

If a participant discontinues the study intervention before the scheduled EOT Visit, then the participant’s 24-hour ambulatory SBP data will be collected as soon as possible. Missing assessments after discontinuation of study intervention due to an AE, lack of efficacy, or any other reason will not be imputed for the primary analysis.

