## 9.5. Sample Size Determination

The sample size is dependent upon the results of the planned interim analysis (refer to Section 9.4). The sample size also accounts for a 60% screen failure rate after enrollment (ie, signing the ICF) during the Screening Period and assumes a 15% discontinuation/withdrawal rate during the Intervention Period. Based on these assumptions, approximately 170 (up to approximately 230) study participants will enroll to enable a minimum of 67 (up to approximately 91) to initiate the study intervention (ie, switch to XYWAV) and to capture complete data (both during the Screening Period and at the EOT Visit) for a minimum of 57 participants (up to approximately 77).

There are no historical data on 24-hour average BP changes in participants switching from twice-nightly high-sodium oxybate to XYWAV. Given the limited information, data from other studies with drugs similar to oxybate were leveraged to inform the design of this study. It was determined that an effect size of 3.0 or 3.5 with a SD range from 7.0 to 8.0 will be considered for power and sample size calculations. Sample sizes for different scenarios (different effect size and SD) were calculated ([Table 6](#)). Power calculations were performed assuming a 1-sided Type 1 error rate of 0.025.

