**Table 6: Power and Sample Size Calculations**

Effect Size	Standard Deviation	80% Power	85% Power	90% Power
3.0	7.0	45	51	60
3.5	7.0	34	38	44
3.0	7.5	52	59	68
3.5	7.5	39	44	51
3.0	8.0	58	66	77
3.5	8.0	43	49	57

A preselected target sample size of 57 completers ( $n_0 = 57$ ) will provide 90% power to detect a difference of 3.5 points in means for the change from the baseline to the EOT Visit (after 6

weeks of treatment on XYWAV) in 24-hour average SBP when switching from twice-nightly high-sodium oxybate to XYWAV, assuming an SD of 8.0 points.

After 75% of participants have completed the study, an interim analysis will be conducted. If the study does not stop early for efficacy, conditional power for the primary endpoint will be calculated, and the adaptive sample size target may be increased up to a maximum of 77 participants (refer to Section [9.4](#)).

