#### 4. ANALYSIS SETS

For purposes of analysis, the following populations are defined:

Analysis Set	Description
Enrolled Set	
The Enrolled Analysis Set will include all participants who provide informed consent for this study.
 
This analysis set will be used to summarize participant disposition, protocol deviations (as classified in Clinical Trial Management Software), and inclusion/exclusion from the Safety Set, including reasons for exclusion from it.

Safety Set	
All participants who take/receive at least 1 dose of study intervention (XYWAV).
 
This analysis set will be used for reporting analyses of safety endpoints.

Completer Set	
All participants who complete the EOT Visit after 6 weeks of study intervention with a 24-hour BP recording at this visit that meets the minimal data standards.
 
This analysis set will be used for primary analyses of effectiveness endpoints.

Effectiveness Set	
All participants who complete at least one post-baseline study effectiveness assessment (including early discontinuation).
 
This analysis set will be used for reporting sensitivity analyses of effectiveness endpoints.

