#### **7.1.1. Primary Analysis**

An analysis of covariance (ANCOVA) model will be used to estimate the primary efficacy endpoint using the SAS PROC MIXED procedure on the Completer Set. The model will include the change in 24-hour SBP from baseline to EOT Visit as the dependent variable and the mean-centered baseline 24-hour SBP as an independent variable in the model.

$$\text{BASE\_CENTERED} = \text{BASE} - \overline{\text{BASE}}$$

Example SAS Code for the ANCOVA model is shown below:

```
proc mixed data = DSET;  
  class avisitn;  
  where avisitn = [EOT];  
  model chg = base_centered avisitn;  
  lsmeans avisitn;  
run;
```

Least-squares mean change from baseline (LS-mean), standard error (SE), 95% confidence interval, and *p*-value will be reported. Unadjusted values at each visit, including change from baseline, will also be summarized as continuous variables.

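### The primary and secondary tests use completers only, although the stated estimands include participants who discontinue treatment

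*Protocol*

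**What the plan says.** **Estimand.** Protocol 1.1 and 3 list stopping treatment, for any reason, among the intercurrent events of the primary and all three secondary estimands. They then state: "Participants who experience any intercurrent event will be included in the analysis". Protocol 9.3.1.2 adds: "A Treatment Policy strategy will be used for each specified analysis".

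**Data collection.** This follows the estimand. Protocol 7.1 asks participants who stop study intervention to stay, where possible, for the second 24-hour recording. Section 9.3.1.2 asks for their ambulatory SBP promptly. The E/D column of both schedules (Tables 3 and 4) includes 24-hour BP monitoring.

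**Analysis.** Protocol 9.2 defines the Completer Set as "All participants who complete the EOT Visit after 6 weeks of study intervention", with a recording at that visit that meets the data standard, and assigns it to the primary analyses. SAP 4 does the same: "This analysis set will be used for primary analyses of effectiveness endpoints". SAP 7.1.1 will "estimate the primary efficacy endpoint using the SAS PROC MIXED procedure on the Completer Set", and its example code keeps only the EOT visit. SAP 7.2.1 uses the same set for the secondary endpoints.

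**Where discontinuers appear.** They are in the Effectiveness Set, which both documents reserve for sensitivity analyses (Protocol 9.2; SAP 4, 7.1.2 and 7.2.2). Protocol 9.2 also allows sensitivity analyses of efficacy on the Safety Set, and SAP 5.2.4 creates last-observed-value records for supplemental use. SAP 5.6 reports no changes to planned analyses.

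**The concern.** A participant who stops XYWAV early and gives a valid recording after the switch belongs in the analysis under the estimand and is excluded from it under the analysis-set definition. Two statisticians could build different primary datasets, each citing the protocol.

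The consequence goes beyond labelling. The primary test alone decides the binding efficacy stop at the interim (Protocol 9.4) and opens the testing hierarchy (Protocol 9.1.1). It therefore decides what the one confirmatory claim means: the effect of being switched, or the change seen in those who stay on XYWAV for 6 weeks. The study has a single arm, so no between-arm comparison can offset selective loss. If discontinuers fall less than completers, the completer mean is larger than the effect the estimand describes.

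**Working it through.** **1. The plan's own figures.** Inputs from Protocol 9.5: effect 3.5 mm Hg, SD 8.0, power 90%, and "Power calculations were performed assuming a 1-sided Type 1 error rate of 0.025". For a one-sample t-test on the change, power is 1 - F(t[0.975, n-1]; n-1, 3.5√n/8), where F is the noncentral t distribution. The smallest n that reaches 0.90 is 57 (power 0.901), and the same method reproduces all 18 cells of Table 6. So the statement that 57 completers "will provide 90% power to detect a difference of 3.5 points in means" is correct for completers. With 15% loss, 57/0.85 = 67.06 (stated 67) and 77/0.85 = 90.6 (stated 91). The plan thus expects 67 - 57 = 10 treated participants outside the primary analysis, or 91 - 77 = 14 at the maximum size.

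**2. Who is in and who is out.**

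| Participant | Estimand and 9.3.1.2 | Completer Set |
|---|---|---|
| Completes 6 weeks, valid EOT recording | In | In |
| As above, antihypertensive therapy changed | In | In |
| Stops early, valid post-switch recording | In | Out |
| No valid post-switch recording | In, but value missing and not imputed | Out |

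The two rules conflict over an observed value only in the third row.

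**3. How far apart the two means could be.** The documents give no BP change for discontinuers, so x below is an assumption. With completers at -3.5, the all-treated mean is (57 × (-3.5) + 10x)/67. For x = 0 this is -199.5/67 = -2.98; for x = +3.5 it is -164.5/67 = -2.46.

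| Discontinuers' change x (assumed) | All-treated mean | Completer mean relative to it | Power, all 67 measured | N measured for 90% power |
|---|---|---|---|---|
| -7 | -4.02 | 0.52 smaller fall | 0.98 | 45 |
| -3.5 | -3.50 | same | 0.94 | 57 |
| -1.75 | -3.24 | 0.26 larger fall | 0.90 | 67 |
| 0 | -2.98 | 0.52 larger fall | 0.84 | 80 |
| +3.5 | -2.46 | 1.04 larger fall | 0.66 | 125 |

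The power columns use one-sided 0.025 at a single look and a mixture SD of √(64 + p(1-p)(x + 3.5)²), with p = 10/67 for the power column and 0.15 for the N column. For scale, the standard error at N = 67 is 8/√67 = 0.98 mm Hg.

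**4. What this could do to the error rate.** Suppose the true all-treated mean change is 0 and the 15% who discontinue change by +y. Completers then average -0.15y/0.85. For y = 2, 3.5 and 5 (assumed) that is -0.35, -0.62 and -0.88 mm Hg. Protocol 9.1.1 says an O'Brien-Fleming "alpha level of 0.02194 will be used for the final analysis". At a single look with 57 completers and that level, the test rejects with probability 0.046, 0.075 and 0.116. With y = 0 it rejects at 0.022, as intended. With y negative it rejects less often than the nominal rate.

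**The case against.** The strongest reply is that the completer question is open to view. The target, the interim count and the cap are stated in completers, the hypotheses in Protocol 9.1.1 refer to 6 weeks of XYWAV, and discontinuers are analysed in prespecified sensitivity analyses. That is fair, and it shows the restriction is not hidden. It does not resolve the conflict. The sensitivity analyses carry no formal test, and 9.3.1.2 applies treatment policy to each specified analysis. The no-imputation sentence concerns missing values, whereas the Completer Set also removes observed ones.

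Three stronger readings are tempting, and the documents support none of them.

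- *The completer test is biased in the drug's favour.* There are no BP data on discontinuers. If they change as completers do there is no distortion, and if they fall further the completer result is the less favourable one. Nothing in the plan links the reasons for stopping to BP change.
- *Treatment policy is abandoned altogether.* It is kept for changes in antihypertensive therapy among those who complete.
- *Changing the set would recover all 10 participants.* The 15% rate also covers withdrawal from the study, and recordings after discontinuation are sought only where possible. The number recoverable lies somewhere between 0 and about 10.

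One further point stands. SAP 5.2.3 prefers the E/D visit to take place while the participant is still on treatment. Pooling such early recordings with week-6 recordings mixes exposure times and does not by itself estimate a week-6 treatment-policy effect.

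**Conclusion.** The contradiction is in the text and needs correcting: the estimands and 9.3.1.2 include treatment discontinuers, and the primary and secondary tests exclude them even when a valid recording exists. The sample size of 57 is not an arithmetic error; it is correct for completers.

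The completer result is probably the more favourable one if discontinuers fall less than completers, which is plausible under the trial's own hypothesis because completers have had the full period of reduced sodium. That direction is not established. The difference of 0.5 to 1.0 mm Hg, for discontinuers at 0 to +3.5, is a bound. It rests on the plan's 15% rate, completers at -3.5, assumed discontinuer values, and a comparison with the mean of all treated participants. A wider analysis set would close the gap only for those with a valid recording.

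**What to change.** Choose one option before the primary test is first run, which means before the interim analysis if that is still to come.

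**(a) Align the analysis with the estimand.** In Protocol 9.2 and 9.3.2 and SAP 4, 7.1.1 and 7.2.1:

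- Make the primary set all treated participants with a valid baseline and a valid post-switch 24-hour recording.
- State which recording represents a discontinuer, preferring one at about week 6 over an early E/D recording where both exist.
- Keep the Completer Set as the supportive analysis.
- Add a conservative sensitivity analysis for participants with no post-switch recording, for example with change set to 0.
- Restate the items now built on completers: the interim trigger (43), target (57), cap (77) and conditional-power inputs, the sleep-diary thresholds in SAP 7.2.1, and the EOT filter in the example code.

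The recordings are already scheduled, so no new assessment is needed. The estimate may be somewhat smaller, and the stated 90% power at 57 would then apply to completers only.

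**(b) Align the estimand with the analysis.** Restate the primary and secondary estimands as completer (on-treatment) estimands. Remove the treatment-policy wording for discontinuation from Protocol 1.1, 3 and 9.3.1.2. Limit the conclusion to participants who complete 6 weeks on XYWAV. This changes wording only and leaves the sample size intact. Its price is a narrower claim, with discontinuers covered only by the sensitivity analyses.
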